## Worsening of Cytokine Release Syndrome

There is limited experience with mavrilimumab or other anti-GM-CSF agents in patients with COVID-19. In the expanded access protocol conducted by Italian investigators with mavrilimumab (De Luca G, 2020), all except for one of the subjects treated with mavrilimumab experienced a decrease in CRP and IL-6. Given the limited experience, in this study [worsening of] cytokine release syndrome (CRS) will be assessed as an AESI and should be reported within 24 hours of knowledge of the event. If a suspected CRS occurs, eg, symptoms such as malaise, nausea and vomiting, diarrhea, unscheduled blood sample kits should be collected, which will include serial cytokines and inflammatory biomarkers. These samples should be immediately shipped to the central laboratory and the study site should collect local available cytokines and inflammatory biomarkers in parallel.

### 12.2.1.4. Serious Adverse Event (SAE)

An SAE is defined as any AE (appearance of [or worsening of any pre-existing] undesirable sign(s), symptom(s) or medical condition(s)) which meets any one of the following criteria:

- results in death
- is life-threatening
  - Life-threatening in the context of a SAE refers to a reaction in which the subject was at risk of death at the time of the reaction; it does not refer to a reaction that hypothetically might have caused death if it were more severe (please refer to the ICH-E2D Guidelines)
- results in persistent or significant disability/incapacity
- constitutes a congenital anomaly/birth defect
- requires inpatient hospitalization or prolongation of existing hospitalization, unless hospitalization is for:
  - routine treatment or monitoring of the studied indication, not associated with any deterioration in condition (coronary heart disease, cerebrovascular disease or peripheral vascular disease)

- elective or pre-planned treatment for a pre-existing condition that is unrelated to the indication under study and has not worsened since signing the informed consent
- social reasons and respite care in the absence of any deterioration in the subject's general condition
- treatment on an emergency outpatient basis for an event not fulfilling any of the definitions of a SAE given above and not resulting in hospital admission
- is medically significant, eg, defined as an event that jeopardizes the subject or may require medical or surgical intervention to prevent one of the outcomes listed above.

Medical and scientific judgment should be exercised in deciding whether other situations should be considered serious reactions, such as important medical events that might not be immediately life threatening or result in death or hospitalization but might jeopardize the subject or might require intervention to prevent one of the other outcomes listed above. Such events should be considered as “medically significant”. Examples of such events are intensive treatment in an emergency room or at home for allergic bronchospasm, blood dyscrasias or convulsions that do not result in hospitalization or development of dependency or abuse.

All malignant neoplasms will be assessed as serious under “medically significant” if other seriousness criteria are not met.

Any suspected transmission via a medicinal product of an infectious agent is also considered a serious adverse reaction.

All reports of intentional misuse and abuse of the product are also considered serious AE irrespective of whether a clinical event has occurred.

### **12.3. Relationship to Study Drug**

An Investigator who is qualified in medicine must make the determination of relationship to the investigational product for each AE (Not Related, Unlikely Related, Possibly Related or Definitely Related). The Investigator should decide whether, in his or her medical judgment, there is a reasonable possibility that the event may have been caused by the investigational product. If no valid reason exists for suggesting a relationship, then the AE should be classified as “Not related.” If there is any valid reason, even if undetermined, for suspecting a possible cause-and-effect relationship between the investigational product and the occurrence of the AE, then the AE should be considered “related.”

If the relationship between the SAE and the investigational product is determined to be “Possibly” or “Definitely” related, the event will be considered related to the investigational product for the purposes of expedited regulatory reporting. If the relationship between the SAE and investigational product is deemed to be “unlikely related,” the case is considered expedited in Japan but not expedited in the USA or European Union.

### **12.4. Recording Adverse Events**

The Investigator has the responsibility for managing the safety of individual subject and identifying AEs.

Qualified medical personnel will be readily available to advise on trial related medical questions or problems.

The occurrence of AEs must be sought by non-directive questioning of the subject at each visit during the study. AEs also may be detected when they are volunteered by the subject during or between visits or through physical examination findings, laboratory test findings, or other assessments.

AEs must be recorded in the Adverse Events CRF under the signs, symptoms or diagnosis associated with them, accompanied by the following information (as far as possible) (if the event is serious refer to Section 12.2.1.4):

1. The severity grade:
  - mild: usually transient in nature and generally not interfering with normal activities
  - moderate: sufficiently discomforting to interfere with normal activities
  - severe: prevents normal activities.
2. Its relationship to the study treatment. If the event is due to lack of efficacy or progression of underlying illness (ie, progression of the study indication) the assessment of causality will usually be 'Not suspected'. The rationale for this guidance is that the symptoms of a lack of efficacy or progression of underlying illness are not caused by the trial drug, they happen in spite of its administration and/or both lack of efficacy and progression of underlying disease can only be evaluated meaningfully by an analysis of cohorts, not on a single subject.
3. Its duration (start and end dates) or if the event is ongoing, an outcome of not recovered/not resolved must be reported.
4. Whether it constitutes a SAE (see Section 12.2.1.4 for definition of SAE) and which seriousness criteria have been met.
5. Action taken regarding with study treatment.

All AEs must be treated appropriately. This study includes a single IV dose administration. No dose adjustment is anticipated. Actions may include:

  - Not applicable
  - Dose temporarily interrupted but later completed
  - Dose interrupted and not completed
6. Its outcome
  - not recovered/not resolved
  - recovered/resolved
  - recovering/resolving
  - recovered/resolved with sequelae
7. fatal; or unknown.

Conditions that were already present at the time of informed consent should be recorded in the medical history of the subject.

AEs (including lab abnormalities that constitute AEs) should be described using a diagnosis whenever possible, rather than individual underlying signs and symptoms.

AE monitoring should be continued for at least 60 days following the last dose of study treatment.

Once an AE is detected, it must be followed until its resolution or until it is judged to be permanent (eg, continuing at the end of the study), and assessment must be made at each visit (or more frequently, if necessary) of any changes in severity, the suspected relationship to the interventions required to treat it, and the outcome.

The Medical Dictionary for Regulatory Activities (MedDRA) will be used to code all AEs.

## **12.5. Reporting Serious Adverse Events**

To ensure subject safety, every SAE, regardless of causality, occurring after the subject has provided informed consent and until the last study visit must be reported to the Sponsor or designee, within 24 hours of learning of its occurrence. Additionally, Investigator reporting of SAEs to IRB/EC and other Regulatory Health Authorities may be required per local rules and regulations. For the purpose of determining the expectedness of Serious Suspected Adverse Reactions in ongoing studies conducted by Kiniksa, the following Serious Suspected Adverse Reaction is considered an expected reaction: Pneumonia.

More specifically, the Investigator will report all SAEs to the Kiniksa Pharmaceuticals safety CRO vendor no later than 24 hours after the Investigator's initial receipt of this information.

The event must also be recorded on the clinical database. Preliminary reports of SAEs must be followed by detailed descriptions as soon as possible including clear and redacted photocopies of hospital case reports, consultant reports, autopsy reports, and other documents when requested as applicable and if available.

If the SAE is not previously documented in the Investigator's Brochure and is thought to be related to the study treatment, then the event is considered a suspected unexpected serious adverse reaction (SUSAR), and Kiniksa or designee may need to issue an Investigator Notification to inform all Investigators involved in any study with the same study treatment that this SAE has been reported. The standard timelines for SUSAR reporting as per ICH E2A will be followed.

The Sponsor or designee will report all SUSARs to the applicable Regulatory Authorities no later than 15 calendar days after the Sponsor's initial receipt of this information. Fatal or life-threatening unexpected experiences for which there is a possibility that the experience may have been caused by the drug will be reported by the Sponsor or designee to the Regulatory Authorities by telephone or facsimile transmission no later than 7 calendar days after receipt of this information.

Any SAEs experienced after completion of the study should only be reported to the Sponsor/Investigator.

## Exceptions to SAE Reporting

Events that are captured as protocol-mandated clinical outcome measures (ie, part of the 8-point NIAID scale) should not be reported as SAEs. This would include initiation of invasive mechanical ventilation and/or ECMO, non-invasive ventilation or high-flow oxygen, and supplemental oxygen. In addition, procedures associated with these clinical outcome measures (eg, intubation or tracheostomy) should not be reported as SAEs. Events that in the judgment of the investigator are clearly a part of the natural history of severe COVID-19 pneumonia with hyper-inflammation should not be reported as SAEs (eg, fever, elevated CRP). All deaths, serious infections and severe granulocytopenia and neutropenia should be reported as SAEs. Per the Investigator Brochure, pneumonia is the only event that is included in the Reference Safety Information (RSI) and would be considered expected or listed. Any other serious related adverse drug reactions would be considered unexpected and would require expedited reporting.

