**The efficacy and safety results from the KPL-301-C203, Phase 2 Cohort 1 subjects**, support use of both doses of mavrilimumab in the ongoing Phase 3 study. While generally there are no apparent differences between the two mavrilimumab arms for efficacy and safety, given the small number of primary events of ventilation and/or death analyzed to date, there are some differences between the two doses in mortality (10 mg/kg is numerically efficacious) or ventilation-free survival (6 mg/kg is numerically more efficacious). Overall, both the 10 mg/kg and the 6 mg/kg appear well-tolerated with no new identified safety risks in the COVID-19 study population. In fact, serious infections (e.g., septic shock, sepsis) were substantially lower in both mavrilimumab dose arms compared to placebo, and thrombosis events were only reported in the placebo arm. There were no serious adverse events related to mavrilimumab, no dose-related adverse events and no infusion reactions.

**Important potential risks for mavrilimumab** will continue to be monitored. These include severe hypersensitivity reactions, immune complex disease, serious infections (viral, bacterial, and opportunistic infections), malignancy, vaccine interactions, pulmonary alveolar proteinosis, reproductive toxicity and granulocytic effects, including neutropenia. Of note, there is no biological rationale for several of these potential risks in the setting of a single dose administration. More importantly, none of these potential risks have been identified in the RA development program through Phase 2b with approximately 900 subject-years of exposure. See Investigator's Brochure for additional details.

This clinical study was designed and shall be implemented, executed, and reported in accordance with the ICH Tripartite Guidelines for Good Clinical Practice, with applicable local regulations, US Code of Federal Regulations (CFR) 21, and with the ethical principles laid down in the Declaration of Helsinki.

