**Figure 1: Study Design for KPL-301-C203**

A Safety Review Committee (SRC) including 2 physicians from the Sponsor, 1 physician from the Sponsor's contract research organization (CRO), and 1 independent physician who is an expert in critical care medicine, pulmonary disorders, infectious diseases and/or COVID-19 treatment (SRC Chairperson) will meet periodically to review AEs/SAEs, reasons for study discontinuations, and key clinical and laboratory assessments. SRC activities will be guided by an SRC Charter. The initial SRC meeting will be triggered once the initial 4 subjects have completed Day 8. SRC members will be blinded to subject treatment assignment.

A Data Monitoring Committee (DMC) has been established by the Sponsor to conduct periodic reviews and may meet more frequently as needed to review unblinded safety data from the Phase 2 and 3 portions of the study. The initial meeting will be triggered at 1 month after the first subject is enrolled. The DMC charter will detail the composition, roles and responsibilities and analysis plan for the DMC's activities.

The study may be terminated if unexpected, significant, or unacceptable safety risks to enrolled subjects arise, or if recommended by applicable board(s) after review of safety data.

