#### **13.2.7. Interim Analysis**

There is no interim analysis planned for the Phase 2 or Phase 3 part of the study. Instead, the Sponsor will conduct a primary and/or final efficacy analysis (ie, review of unblinded study results) when the last subject in each Phase and Cohort completes the Day 29/Day 90 assessments.

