## 2.4. Safety Endpoints

The following are safety endpoints:

- Adverse events, adverse events of special interest, and serious adverse events
- Laboratory parameters
- Vital signs
- Electrocardiogram
- Chest x-ray or CT scan
- Physical examination

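### The SAE exemption for ventilation and oxygen-support events has no carve-out for events rated drug-related, and so conflicts with the reporting rules around it

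*Combined protocol and SAP*

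**What the plan says.** The general rule in protocol Section 12.5 is that "every SAE, regardless of causality, occurring after the subject has provided informed consent and until the last study visit must be reported". The deadline is 24 hours from when the site learns of the event, and the report goes to the sponsor or its designee. Section 12.3 has the investigator rate each event on a four-level scale. SAEs at the two upper levels, Possibly or Definitely Related, are handled as related for expedited regulatory reporting.

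The subsection Exceptions to SAE Reporting then makes three exemptions:

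- **NIAID-scale events:** "Events that are captured as protocol-mandated clinical outcome measures (ie, part of the 8-point NIAID scale) should not be reported as SAEs". The text continues: "This would include initiation of invasive mechanical ventilation and/or ECMO, non-invasive ventilation or high-flow oxygen, and supplemental oxygen".
- **Procedures** that go with those events, with intubation and tracheostomy as examples.
- **Natural-history events**, where the investigator judges that the event clearly belongs to the course of severe COVID-19 pneumonia.

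Some events are kept in: "All deaths, serious infections and severe granulocytopenia and neutropenia should be reported as SAEs". The subsection closes by naming pneumonia as the only expected reaction. It says that other serious related reactions count as unexpected and need expedited reporting.

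**The concern.** The natural-history exemption depends on the investigator's judgment. The NIAID and procedure exemptions do not. A site that reads them literally would not report a non-fatal intubation as an SAE even if its own investigator had rated it Possibly or Definitely Related.

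Such a rating should be uncommon, since Section 12.4 says that causality for disease progression will usually be recorded as not suspected. An event still rated related is therefore informative, and the exemption drops it from the fast route. The regulatory clock in Section 12.5 (15 calendar days, or 7 for fatal or life-threatening unexpected events) runs from the sponsor's receipt of the information. If the site sends no SAE report, that route does not start the clock.

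**Working it through.** The plan states no figure on this point, so the check is a comparison of the rules, followed by a note on size.

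**1. A test case.** Take a Cohort 1 subject who is intubated well after the infusion and survives. The investigator rates the event Possibly Related and makes no separate diagnosis. There is no infection and no hypersensitivity or cytokine release reaction. Under Section 12.2.1.4 the event can be serious as life-threatening or as prolonging hospitalization.

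| Text | Instruction for this event |
|---|---|
| 12.5, general rule | Report within 24 hours, whatever the causality |
| 12.3 | Treat as related for expedited reporting |
| 12.5 Exceptions, NIAID sentence | Do not report as an SAE |
| 12.5 Exceptions, procedure sentence | Do not report the intubation as an SAE |
| 12.5 Exceptions, closing sentence | Serious, related and not pneumonia: expedited reporting needed |

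The documents do not say which instruction prevails.

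**2. What remains reportable.** These routes are unaffected, and they mark the limits of the gap:

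- All deaths, serious infections, and severe granulocytopenia and neutropenia (12.5 Exceptions).
- Adverse events of special interest, reported within 24 hours regardless of seriousness (12.2.1.3). These include anaphylaxis, severe hypersensitivity, serious or opportunistic infection and worsening cytokine release syndrome.
- Severe infusion reactions, whose examples include hypoxia. Four causally related ones within 24 hours of dosing pause enrollment for DMC review (7.3.1).
- A diagnosed disorder. Section 12.4 asks for a diagnosis wherever possible, and a diagnosis is not a level of respiratory support.

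Ordinary adverse event recording, with severity and causality (12.4), also continues, but it carries no general 24-hour duty.

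**3. What is left.** Non-fatal ventilation, ECMO or oxygen-escalation events, rated Possibly or Definitely Related, that reach the sponsor by none of the routes in step 2.

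**4. Size.** The nearest figures are the Phase 3 Cohort 1 planning rates in Section 13.3.2: 200 per arm, with 87.5% (active) and 74.4% (placebo) alive and free of ventilation. Section 13.3.2 ties the active rate to 6 mg/kg; it is applied here to both doses as an assumption.

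- Placebo: 200 × (1 − 0.744) = 51.2
- Two active arms: 2 × 200 × (1 − 0.875) = 50.0
- Total: 101.2 ventilation-or-death events. With the 581 randomized (Phase 3 SAP 1.4), 101.2 × 581/600 = 98.0.

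The documents do not give the non-fatal share. If it were 25% to 75%, then 101.2 × 0.25 = 25.3 to 101.2 × 0.75 = 75.9 ventilations would be exempt, of any causality. That does not measure the gap. It says nothing about how many would be rated related, it does not remove events reported by another route, and it leaves out escalations to non-invasive ventilation, high-flow or supplemental oxygen. The size of the gap cannot be derived.

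**The case against.** **An exception is meant to override the general rule.** Endpoint events in a severely ill population are exempted so that SAE reporting is not filled with expected disease progression. That is a fair purpose and explains the departure from the general rule for unrelated events. It does not settle related ones, because the closing sentence of the same subsection calls for expedited reporting of serious related reactions.

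**That closing sentence already protects related events.** This is the strongest reply, and it means that a bypass of expedited reporting is not demonstrated. But the sentence follows from which reactions count as expected, whereas the exemption tells the site what to send. The two need to be reconciled.

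**A reader might infer that serious drug-caused respiratory harm goes unreported.** The documents do not support that. What is exempt is a level of support and its procedures, and the routes in step 2 of the working stay open. The same applies to pulmonary alveolar proteinosis, listed in Section 4 among the potential risks ("vaccine interactions, pulmonary alveolar proteinosis, reproductive toxicity and granulocytic effects, including neutropenia"). It is not an adverse event of special interest, but nothing exempts it once diagnosed.

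**A reader might infer that the exceptions contradict themselves on death**, since death is score 1 on the scale. The examples of exempt events omit death, and the later sentence requires all deaths to be reported. The specific text settles it.

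**A reader might infer that the DMC does not see ventilation by arm.** Section 6.1 has it "review unblinded safety data from the Phase 2 and 3 portions of the study", Phase 3 SAP Section 2.4 does not list NIAID status among the safety endpoints, and Section 13.2.7 says: "There is no interim analysis planned for the Phase 2 or Phase 3 part of the study". But Section 6.1 leaves the DMC's analysis plan to a charter that is not among the documents, and Section 6.5 refers to board review of safety and/or efficacy data. The SAP list does not define the DMC's tables. The sponsor also reviewed unblinded Phase 2 results. What the DMC receives in Phase 3 is unknown, so no deficiency is shown.

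**Conclusion.** The point holds in limited form. The NIAID and procedure exemptions contain a stated rule that conflicts with the general rule in Section 12.5, with Section 12.3 and with the last sentence of the exceptions text. This is more than missing detail: a site following the exemption literally would withhold an SAE report that other sentences call for.

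The conflict is confined to the residual group in step 3 of the working. The conclusion rests on the wording alone and on the assumption that the separate manuals and the DMC charter, which are not available here, do not already resolve it. The count of about 101 expected ventilation-or-death events shows how often the exemption could come into play, but it does not estimate how many drug-suspected events would be missed.

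**What to change.** In Section 12.5, Exceptions to SAE Reporting, add a clause to both the NIAID-scale and the procedure exemptions, for example: *These exemptions do not apply when the Investigator rates the event Possibly or Definitely Related to study drug; such an event is reported as an SAE under the 24-hour rule of Section 12.5.* This brings the exemptions into line with Section 12.3 and with the closing sentence of the subsection.

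The cost is one clause in an amendment and a few more SAE reports. The number should be small, because Section 12.4 already steers disease progression away from a related rating.

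As a secondary suggestion only, confirm in Section 6.1 or the DMC charter whether the DMC sees Phase 3 ventilation and NIAID status by arm. Ventilation mode and NIAID score are already recorded daily until discharge (Section 10.4.1 and Table 2), so a table would need no new data collection.
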